5.2. Exclusion Criteria

Patients who meet any of the following exclusion criteria will be excluded from participation in the study:

- 1. History of suicide attempt in the past 2 years or within current MDD episode.
- 2. Active suicidal ideation with plan or a "yes" response to items 4 or 5 on the C-SSRS in the past 24 months is exclusionary as assessed at Screening and Baseline (Day 1).
- 3. Inadequate response to >2 prior ADTs (not including current antidepressant) of at least 6 weeks duration each for the episode current at screening.
- 4. Recent history or active clinically significant manifestations of metabolic, hepatic, renal, hematological, pulmonary, cardiovascular, gastrointestinal, musculoskeletal, dermatological, urogenital, neurological, ophthalmic (especially cataracts), or ears, nose, and throat (ENT) disorders, or any other acute or chronic condition that, in the Investigator's opinion, would limit the subject's ability to complete or participate in this clinical study.
- 5. Based on an ophthalmic examination performed at Screening, patient must not have any of the following:
 - Nuclear opalescence (NO) with a LOCSIII classification > 3.0 in either eye
 - Nuclear color (NC) with a LOCSIII classification > 3.5 in either eye
 - Cortical lens opacities (C) with a LOCSIII classification > 2.0 in either eye
 - Posterior subcapsular lens opacities (P) with a LOCSIII classification > 0.3 in either
- 6. History or presence of intellectual disability, pervasive developmental disorder, cognitive disorder, neurodegenerative disorder (e.g., Alzheimer's disease, Parkinson's disease, multiple sclerosis, Huntington's disease), or brain injury.

- 7. Receipt of electroconvulsive therapy (ECT) within 12 months of screening, lifetime receipt of more than one course of ECT, or plans to receive ECT during the study.
- 8. Receipt of repetitive transcranial magnetic stimulation (rTMS) within 12 months of screening or planned to receive rTMS during the study.
- 9. Plans to initiate or terminate cognitive or behavioral psychotherapy or alter the frequency of ongoing therapy during this study.
- 10. Works night shifts or needs to work night shifts during the study.
- 11. Females who are pregnant, intend to become pregnant (within 90 days of the last dose of ANC-501), are breastfeeding, or have a positive pregnancy test at screening or on Day 1 prior to study drug administration.
- 12. Known allergy to ANC-501, or related compounds.
- 13. Detectable hepatitis B surface antigen (HBsAg), hepatitis C virus antibody (HCV Ab), or human immunodeficiency virus (HIV) antibody at screening.
- 14. Active psychosis per Investigator assessment.
- 15. Medical history of seizures (does not include isolated febrile seizures of childhood).
- 16. Medical history of bipolar disorder, schizophrenia, and/or schizoaffective disorder.
- 17. History of alcohol or substance use disorder in the 12 months prior to screening.
- 18. Positive alcohol breath test.
- 19. Positive urine drug screen for hallucinogens, psychoactive inhalants, stimulants, opioids, barbiturates, non-prescribed anxiolytics or other non-prescribed sedatives. Does not include positive test for cannabinoids, tobacco or caffeine, unless the subject meets criteria for substance use disorder for these substances.
- 20. Exposure to another investigational medication or device within 30 days or 5 half-lives (whichever is longer) prior to screening.
- 21. Has been previously treated in this study or randomized or treated in any other study employing ANC501 (i.e., subject may not have received study drug and then reenrolled).
- 22. Administration of drugs to treat psychiatric or neurologic conditions that have not been taken at a stable dose for at least 4 weeks prior to day 1.
- 23. Need/plan to take moderate to strong inhibitors and/or inducers of cytochrome P450 (CYP)3A4 (food, beverages, medications, and supplements).
- 24. Any condition not identified in the protocol that in the opinion of the Investigator would confound the evaluation and interpretation of the study data or may put the subject at risk.

5.3. Subject Enrollment

Subject eligibility must be verified prior to enrollment. Upon eligibility verification, subject information will be entered into an Interactive Response Technology (IRT) system. The first dose of study drug should be administered within 72 hours (all efforts should be made to initiate

treatment as soon as possible after registration) following entry into the IRT. The date the first dose of study drug is administered is the date the subject is considered enrolled into the study.

5.4. Screen Failures

Screen failures are defined as subjects who consent to participate in the clinical study but not subsequently enrolled in the study. A minimal set of screen failure information is required to ensure transparent reporting of screen failure subjects to meet the Consolidated Standards of Reporting Trials (CONSORT) publishing requirements and to respond to queries from regulatory authorities. Minimal information includes demography, screen failure details, eligibility criteria, and any serious adverse event (SAE) that occurs after completion of the informed consent form (ICF).

Subjects who do not meet the criteria for participation in this study (i.e., screen failures) may be rescreened after discussion with the Medical Monitor. Previously completed study assessments remaining within the protocol-defined window will be accepted for rescreening.

6. STUDY TREATMENT

6.1. Study Treatment Administered

Subjects will receive 50 mg ANC-501 Capsules (5×10 mg capsules) orally once daily at least 1 hour prior to the morning meal for 8 weeks beginning with the first dose administered in the clinic on Day 1.

6.2. Handling, Storage, and Accountability

ANC-501 Capsules are stored in child-resistant 35-count bottles at controlled room temperature (15–25°C/59–77°F).

The Investigator or designee must confirm appropriate temperature conditions have been maintained during transit for all study drug received, and any discrepancies are reported and resolved before use of the study drug.

Only subjects enrolled in the study may receive study drug, which may only be supplied or administered by authorized site staff. All study drug must be stored in a secure, environmentally controlled, and monitored (manual or automated) area in accordance with the labeled storage conditions, with access limited to the Investigator and authorized site staff.

The Investigator is responsible for study drug accountability, reconciliation, and record maintenance (i.e., receipt, reconciliation, and final disposition records). The Investigator or designee will maintain a record of all study drug received and dispensed.

Further guidance and information for the final disposition of unused study drug are provided in the Pharmacy Manual.

6.3. Measures to Minimize Bias: Randomization and Blinding

Not applicable; this is an open-label study.

6.4. Treatment Compliance

Drug accountability will be performed by the study site using appropriate source documentation and recorded in the eCRF.

6.5. Dose Modifications

During the Open-Label Treatment Period, subjects will be able to receive study drug as long as there are no dose-limiting safety/tolerability concerns as determined by the Investigator. Subjects who experience moderate or severe AEs while receiving the 50 mg dose of study drug which, according to the clinical judgement of the Investigator, are related to study drug, may receive 40 mg for the remainder of the Open-Label Treatment Period if the AEs are intolerable. Subjects who experience moderate or severe related AEs while receiving the 40 mg dose of study drug might not be able to continue receiving study drug based on the evaluation and clinical judgment of the Investigator and may be discontinued from further treatment.

6.6. Continued Access to Study Drug after the End of Study

There are currently no plans to provide ANC-501 to subjects after the study ends.

6.7. Treatment of Overdose

No information regarding overdose of ANC-501 in humans is available. The subject should be closely monitored for signs of toxicity, and the Medical Monitor notified immediately. There is no specific antidote for overdose of ANC-501, and general supportive care should be provided.

6.8. Concomitant Medications and Therapies

Any medication or vaccine(s) (including over-the-counter or prescription medicines, recreational drugs, vitamins, and/or herbal supplements) that the subject received within 30 days prior to informed consent or receives during the study must be recorded along with the reason for use, start and end dates, dose, and frequency. The Medical Monitor should be contacted if there are any questions regarding prior or concomitant therapy.

Subjects may not have received another investigational medication or device within 30 days prior to screening. Psychotropic medications, which must have been initiated at least 8 weeks prior to screening, must remain at a stable dose until completion of the Day 56 assessments.

Strong inhibitors and/or inducers of CYP3A4 (food, beverages, medications, and supplements) are not permitted.

7. DISCONTINUATION OF STUDY TREATMENT AND SUBJECT WITHDRAWAL

7.1. Discontinuation of Study Treatment

A subject must be discontinued from study treatment for any of the following:

- 1. Unacceptable toxicity, despite maximal supportive care and/or dose reduction.
- 2. Subjects exhibiting a change in the LOCS III greater than or equal to 0.5 in Nuclear Opalescence, Cortical Opalescence or Posterior Subcapsular Opalescence in either eye or clinically significant eye changes (e.g., incident of cataract).
- 3. Investigator decision (may include the need for antidepressant therapy or other therapy not otherwise permitted in the study, including ECT or changes to cognitive/behavioral psychotherapy) or noncompliance with study requirements.
- 4. Subject becomes or intends to become pregnant.
- 5. Subject withdrawal of consent for further study treatment.
- 6. Study termination by the Sponsor.

Subjects discontinuing treatment should complete the Early Termination visit procedures and enter the Follow-up Period.

7.2. Subject Withdrawal from Study

A subject will be withdrawn from all study participation (i.e., discontinued without further follow-up):

- 1. Withdrawal of consent to further follow-up assessments, irrespective of the reason
- 2. Lost to follow-up
 - a. A subject will be considered lost to follow-up after repeated failure to attend scheduled study visits, and who is unable to be contacted by the study site. Only after 3 phone calls (if possible) are attempted and no response received from a certified letter (or equivalent local method) to the subject's last known mailing address should a subject be considered lost to follow-up. All contact attempts should be documented in the subject's source records.
- 3. Death

8. STUDY ASSESSMENTS AND PROCEDURES

Written informed consent must be provided before any study-related procedures/assessments are performed. Refer to the Schedule of Events (Section 1.3) for procedures/assessments and timing.

8.1. General Study Assessments

General study assessments are outlined in Table 1.

Table 1: General Study Assessments

Assessment	Details
Review of inclusion/exclusion criteria	Eligibility is to be confirmed prior to the first dose of study treatment (see Section 5.1 and Section 5.2 for eligibility criteria).
Medical history, demographics	Demographics (age, gender, race, ethnicity), relevant medical history (past and concurrent).
Height and body weight	Height is measured at screening only (for body mass index [BMI] calculation).
Prior and concomitant medications/concomitant therapy	Record all medications that are taken within 30 days prior to informed consent and throughout the study.
Structured Clinical Interview for DSM-5 – Clinical Trials Version (SCID-5-CT) Diagnostic Interview	Subjects will be screened to determine whether they fulfill the criteria for diagnosis of MDD according to the SCID-5-CT, which will be performed by a qualified, trained, validated healthcare professional.
SAFER Interview	The interview will be conducted by a central rater for determination of eligibility. The SAFER inventory for confirmation of eligibility (diagnosis, severity, and treatment history) includes confirmation of MDD using the MADRS, and use of the Massachusetts General Hospital Antidepressant Treatment History Questionnaire (MGH ATRQ) for assessment of current antidepressant therapy (ADT), adequacy of duration and dose of prior and current ADT, as well as degree of improvement, so that only patients with inadequate response (<50% improvement) are included. Site staff will schedule the interview for the central rater, who will contact the patient as scheduled and conduct the interview. Results will be communicated to the site prior to Day 1.
Childhood Trauma Questionnaire (CTQ)	Retrospective measure of childhood trauma containing 5 subscales (emotional abuse, physical abuse, sexual abuse, emotional neglect, and physical neglect). Assessed at screening only.

8.2. Efficacy Assessments

Efficacy assessments are outlined in Table 2.

Table 2: Efficacy Assessments

Assessment	Details
Montgomery-Åsberg Depression Rating Scale (MADRS)	10 questions, each rated on a 7-point scale, to stratify severity of depressive episodes in adults. Includes change from baseline in the MADRS total score at all time points, percentage of MADRS responders (≥50% reduction in total score), percentage of MADRS remitters (total score ≤10).
	The same rater should perform MADRS assessments throughout the study on a given patient when possible.
Hamilton Anxiety Scale (HAM-A)	14 questions, each rated on a 5-point scale, to rate the level of anxiety. Includes change in HAM-A total score from baseline to Day 56, and change in total score at all time points.
Clinical Global Impression-Severity (CGI-S)	7-point scale for clinician to rate the severity of the patient's illness at the time of assessment, relative to past experience with patients having the same diagnosis.
	Includes change in CGI-S total score from baseline to Day 56, and change in total score at all time points.
	The same rater should perform CGI assessments throughout the study on a given patient when possible.
Clinical Global Impression- Improvement (CGI-I)	7-point scale for clinician to assess how much the patient's illness has improved or worsened relative to a baseline state.
	Includes percentage of CGI-I improvers ("Very much improved" or "Much improved") at all time points.
	The same rater should perform CGI assessments throughout the study on a given patient when possible.
Patient Global Impression of Improvement (PGI-I)	7-point scale used to evaluate patient satisfaction with treatment. Includes PGI-I score at Day 56, and score at all time points.
Hamilton Depression Rating Scale (6-item) (HAMD-6)	6-point scale derived from the 17-item Hamilton Rating Scale for Depression to evaluate severity of depression. Subjects will complete the HADM-6 twice a day for three days per week.
General Anxiety Disorder (7-item) (GAD-7)	7-point scale to measure the level of anxiety. Subjects will complete the GAD-7 twice a day for three days per week.
Short Form-Health Survey (36-item) (SF-36)	36-question survey self-reported measure of physical and mental health.
	Includes total score from baseline to Day 56, and change from baseline in total score at all time points.

8.3. Safety Assessments

Safety assessments are outlined in Table 3.

Table 3: Safety Assessments

Assessment	Details
AE monitoring	Serious adverse events (SAEs) that occur subsequent to the signing of the informed consent (i.e., during the Screening Period) as a result of study participation will be recorded. All adverse events (AEs) and SAEs occurring subsequent to the first dose of study drug on Day 1 will be recorded.

Assessment	Details
Physical examination	Physical examination and review of relevant systems at screening, including body weight and height.
Vital signs	Oral temperature (°C), respiratory rate, heart rate, and blood pressure (supine and standing).
12-lead electrocardiograms	A standard 12-lead ECG (ventricular rate, RR, PR, QRS, QT, QTcB, and QTcF) will be performed by the Investigator or designee after the subject has been in the supine position for at least 5 minutes at specified visits. The subject must be in a supine position while the ECG is obtained. Electrocardiogram tracings will be reviewed and interpreted by a qualified clinician. Electrocardiogram tracings and results with Investigator's interpretation are to be included and summarized in the subject's study records.
	The date, time, subject demographics (e.g., age, and sex) and subject number should be recorded on the ECG.
Ophthalmic examination	Ophthalmic exam, including slit-lamp imaging, may be performed by an appropriately trained and qualified individual as delegated by the PI and documented in the Study Delegation Log. However, a licensed ophthalmologist or optometrist must oversee this work and will make the determination on subject eligibility as per inclusion criteria #4. Additional slit lamp imaging of the lenses of both eyes may be performed during the treatment period and sent to a central reader for assessment using the LOCS III as per investigator's discretion. Slit lamp imaging performed during the study showing a change of greater than
	or equal to 0.5 on the LOCS III scale and any changes determined by the investigator to be clinically significant will be recorded and considered an adverse event of special interest.
	Clinical significance is defined as a class I lens event (minimal change) [increase from baseline in the LOCS III grade of ≥ 0.5 (Nuclear Opalescence), ≥ 0.5 (Cortical) or ≥ 0.5 (Posterior Subcapsular)] and any changes considered to be clinically significant (e.g., incidence of cataract).
Columbia-Suicide Severity Rating Scale (C-SSRS)	Rating scale used to assess suicidal ideation and behavior.
	The "Baseline/Screening" C-SSRS form will be completed at screening. The "Since Last Visit" C-SSRS form will be completed at any time of day at all subsequent time points.
Safety laboratory tests	See Table 4.

Abbreviations: AE = adverse event; ECG = electrocardiogram; ET = Early Termination; PK = pharmacokinetic; QTcF = QT interval corrected for heart rate using Fridericia's formula.

8.3.1. Laboratory Assessments

See Table 4 for the list of clinical laboratory tests to be performed and the Schedule of Events (Section 1.3) for timing and frequency.

Table 4: Laboratory Assessments

Laboratory Test	Parameters
Hematology	Hemoglobin, hematocrit, RBC (including mean corpuscular hemoglobin, mean corpuscular volume, mean corpuscular hemoglobin concentration), WBC with differential (neutrophils [absolute count] and lymphocytes, monocytes, eosinophils, basophils), and platelet count.

Laboratory Test	Parameters
Coagulation	PT, INR, aPTT.
Serum chemistry	Non-fasting: albumin, alanine aminotransferase (ALT), aspartate aminotransferase (AST), alkaline phosphatase, amylase/lipase, bicarbonate, bilirubin (total and direct), BUN (urea where BUN not tested), calcium, chloride, creatinine, glucose, magnesium, phosphorus, potassium, sodium, and total protein. Subjects found to have treatment-emergent laboratory toxicity of Grades 3 or 4 will be monitored at least weekly until resolution.
Urinalysis	pH, protein, ketones, bilirubin, nitrite, blood, leukocytes, specific gravity, urobilinogen. Reflex to microscopic exam when positive for protein, blood, nitrite, or leukocytes.
Pregnancy test	Urine pregnancy test will be conducted in only female subjects of childbearing potential. Female subjects who prematurely discontinue will have a pregnancy test performed at the ET visit.
Serology	HBsAg, HCV Ab, HIV antibody
Urine drug and alcohol screen	Urine toxicology for selected drugs of abuse (barbiturates, amphetamines, cocaine, opioids) and breath test for alcohol.
Plasma, saliva, and 12-hour urine collection for measurement of cortisol level,	Study site personnel will dispense the equipment and train subjects on how to collect a 12-hour urine collection for measuring cortisol level. Saliva collection at screening should be a morning sample.

Abbreviations: ALT = alanine aminotransferase; aPTT = activated partial thromboplastin time; AST = aspartate aminotransferase; BUN = blood urea nitrogen; ET = early termination; HBsAg = hepatitis B surface antigen; HCV Ab = hepatitis C virus antibody; HIV = human immunodeficiency virus; INR = International Normalized Ratio; PT = prothrombin time; RBC = red blood cell; WBC = white blood cell.

8.3.1.1. Reporting and Evaluation of Laboratory Test Results

Adverse events will be collected from the first dose of ANC-501, therefore the screening laboratory results are considered baseline. All laboratory test results (except for those at screening, which are considered baseline) must be reviewed for clinical significance by the Investigator. Laboratory test results outside the normal range (hematology, coagulation, chemistry, urinalysis) that worsen in severity from baseline and are deemed clinically significant by the Investigator should be reported as AEs. A new laboratory abnormality resulting in study drug interruption, dose reduction, treatment discontinuation, intervention, or otherwise having an impact on the subject should be reported as an AE, unless it is part of a clinical diagnosis already reported as an AE.

All laboratory values outside the normal range are to be evaluated.

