Abbreviations: AE = Adverse Event; BMI = body mass index; CGI-I = Clinical Global Impression-Improvement; CGI-S = Clinical Global Impression-Severity; C-SSRS = Columbia-Suicide Severity Rating Scale; CTQ = Childhood Trauma Questionnaire, 28-item; ECG = electrocardiogram; ET = early termination; HAM-A = Hamilton Anxiety Rating Scale; HIV = human immunodeficiencyvirus; LOCS III= Lens Opacities Classification System III; MADRS = Montgomery-Åsberg Depression Rating Scale; MDD = major depressive disorder; MGH ATRQ = Massachusetts General Hospital Antidepressant Treatment Response Questionnaire; PGI-I = Patient Global Impression of Improvement; PK = pharmacokinetic; SAE = serious adverse event; SAFER = State vs trait, Assessability, Face and Ecological validity, Rule of 3Ps (pervasive, persistent, and pathological); SCID-5-CT = Structured Clinical Interview for DSM-5 - Clinical Trials Version; HAMD-6= Hamilton Depression Rating Scale (6-item); GAD-7= General

Study Procedure		Screening Period	Open-Label Treatment Period ^a				Follow-up Period ^b			
	Visit Days Window	-30 to -1	Day 1	Day 8 (±3 days)	Day 15 (±3 days)	Day 29 (±3 days)	Day 43 (±3 days)	Day 56/ET (±3 days)	Day 70 (±3 days)	Day 112 (±3 days)

Anxiety Disorder (7-item); SF-36 = Short Form-Health Survey (36-item).

Schedule of Events (continued)

Refer to Section 8 for additional details regarding assessments/procedures.

- a. Subjects who discontinue study treatment before completing the study and those who prematurely withdraw from the study for any reason should undergo Day 56 visit procedures in-clinic as soon as possible and schedule the Day 70 safety assessments (at +2 weeks post ET visit) and Day 112 follow-up ophthalmic visit (at +8 weeks post ET visit).
- b. Subjects will return to the site on Day 70 and 112 for a follow-up visit.
- c. Day 1 procedures are to be completed prior to dosing, except for sparse PK sampling which will be performed prior to dosing and between 0.75 and 2 hours post-dose.
- d. Body weight and height will be measured at screening and BMI will be calculated. Only body weight and BMI calculation will be performed at subsequent visits.
- e. Vital signs include oral temperature (°C), respiratory rate, heart rate, and blood pressure (supine and standing).
- f. Safety laboratory tests will include hematology, serum chemistry, coagulation, and urinalysis. Refer to Table 4 for details.

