5.1. Inclusion Criteria

Patients who meet ALL the following inclusion criteria will be eligible to participate in the study:

- 1. Demonstrate understanding of the study procedures, restrictions, and willingness to participate as evidenced by voluntarily signing and dating the written informed consent form.
- 2. Adult male or female between 18 and 65 years of age, inclusive.
- 3. Good physical health and has no clinically significant findings, as determined by the Investigator, on physical examination, 12-lead electrocardiogram (ECG), vitals, or clinical laboratory tests.
- 4. Has no clinically significant findings on the ophthalmic examination, including Best Corrected Visual Acuity (BCVA) worse than 20/30 or, in the opinion of the ophthalmologist or optometrist, any cataract that may become clinically significant and/or need surgical intervention during the course of the trial.
- 5. Able and willing to complete all study requirements.
- 6. Diagnosis of current episode of major depressive disorder (MDD) at least 8 weeks prior to screening confirmed by Structured Clinical Interview for DSM-5 Clinical Trials Version (SCID-5-CT).
- 7. Have not responded to their current antidepressant therapy or to dose adjustment/treatment changes following a loss of response to their current antidepressant therapy.
- 8. Complete the SAFER interview, administered via teleconference by a Massachusetts General Hospital (MGH) psychiatrist or psychologist, and receive a passing score which confirms a diagnosis of MDD, and a minimum Montgomery-Åsberg Depression Rating Scale (MADRS) total score of 26. The SAFER interview will also confirm the subject's treatment history and response to antidepressant therapies (ADTs) through the administration of the MGH Antidepressant Treatment Response Questionnaire (ATRQ).
- 9. Receiving a stable dose of the same antidepressant (selective serotonin reuptake inhibitor [SSRI], serotonin and norepinephrine reuptake inhibitor [SNRI], bupropion or trazodone monotherapy) for the current episode for at least 6 weeks of continuous treatment, which can include some or all of the screening period, with 4 weeks on a stable dose prior to day 1 and has an inadequate response (<50% improvement) using the MGH ATRQ.
- 10. Willing to maintain stable dose and delay start of other antidepressant or antianxiety medications and any new pharmacotherapy regimens, including benzodiazepine anxiolytics, during the screening and treatment periods.

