## **5.2. Definitions**

- The baseline measurement for a variable is defined as the most recent non-missing value prior to study treatment.
- The change from baseline measurement for a variable at a post-baseline visit will be derived as the measurement taken at the specified visit minus the baseline measurement.
- Treatment Duration will be derived as the total number of days on treatment as follows: Date of Last Dose – Date of First Dose + 1.

- Study Duration will be defined as the total number of days in the study as follows: Date of Last Visit – Date of Informed Consent + 1.
- Treatment Period is defined to be the period that the subject is active on treatment: Date of First Dose through Date of Last Dose.
- Treatment Compliance over the Treatment Period will be calculated as follows based on drug accountability: Treatment Compliance (%) = Number of capsules taken / Number of capsules expected to be taken  $\times$  100.
- Morning Meal Compliance over the Treatment Period will be calculated as follows based on Day 1 administration and the dosing diary: Morning Meal Compliance is Yes if all responses to the following questions are yes; otherwise, Morning Meal Compliance is No:
  - Was subject dosed at least 1 hour prior to morning meal?
  - Since last visit, has subject been compliant with dosing at least 1 hour prior to the morning meal?
- MADRS responders are defined as subjects who experienced a  $\geq$  50% reduction in MADRS total score compared to baseline.
- MADRS remitters are defined as subjects with a MADRS total score  $\leq$  10.
- CGI-I improvers are defined as subjects who reported “Very much improved” or “Much improved” on the CGI-I scale.
- An adverse event is defined as Related if the event is reported as Definitely Related, Probably Related, or Possibly Related.
- Adverse Events of Special Interest are defined as a change from baseline of  $\geq$  0.5 in Nuclear Opalescence, Cortical Lens Opacity, or Posterior Subcapsular Lens Opacity on the LOCS III scale, or any other ophthalmic results deemed clinically significant by the investigator.
- Age at First MDD Diagnosis will be calculated as follows: Year of the First MDD Diagnosis – Year of Birth, where the Year of the First MDD Diagnosis is defined as the year from the earliest start date of the major depressive episodes determined in Section 7.4 of this SAP.

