#### **9.2.4. Clinical Laboratory Tests**

Laboratory evaluations (hematology, serum chemistry, coagulation, urinalysis) will be conducted at Screening, Day 1, Day 8, Day 56, and Day 70. Any clinically significant laboratory result after baseline is to be captured as an adverse event and thus included in the summary of adverse events.

Summary statistics for the observed and change from baseline continuous laboratory results will be displayed at baseline and all scheduled post-baseline visits via the following tables:

- Hematology
- Serum Chemistry
- Coagulation
- Urinalysis

For categorical urinalysis results, frequency counts and percentages will be presented.

For laboratory parameters (hematology, serum chemistry, coagulation) where normal ranges are available, shift tables will be presented for all scheduled post-baseline visits. Categories for the shift tables will be Missing, Low, Normal, High, and Total.

A listing for each category of laboratory results shown in the above bulleted list as well as a listing for serology will also be provided, and values will be flagged as Low, Normal, or High relative to normal ranges, if available, and included in the listings. In addition, a listing will be provided for urine drug screen results and a listing will be provided for alcohol breath test screen results.

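### Protocol 8.3.1.1 judges laboratory AEs against Screening while the SAP uses the last pre-dose value (Day 1), so an abnormality that arose before any drug can be counted as treatment-emergent

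*Protocol*

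**What the plan says.** **Protocol, section 8.3.1.1.** The baseline for laboratory AE reporting is fixed as follows: "Adverse events will be collected from the first dose of ANC-501, therefore the screening laboratory results are considered baseline". The section continues: "All laboratory test results (except for those at screening, which are considered baseline) must be reviewed for clinical significance by the Investigator". Out-of-range results "that worsen in severity from baseline and are deemed clinically significant by the Investigator should be reported as AEs".

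**SAP, section 5.2.** One definition covers every variable: "The baseline measurement for a variable is defined as the most recent non-missing value prior to study treatment". SAP section 9.2.4 makes no exception for laboratory data.

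**Schedule.** SAP section 9.2.4: "Laboratory evaluations (hematology, serum chemistry, coagulation, urinalysis) will be conducted at Screening, Day 1, Day 8, Day 56, and Day 70". A footnote to the protocol's Schedule of Events (section 1.3) says: "Day 1 procedures are to be completed prior to dosing, except for sparse PK sampling". The SAP's Table 1 carries the same footnote. The screening period runs from Day -30 to Day -1.

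**Trigger in the SAP.** Section 9.2.4 also says: "Any clinically significant laboratory result after baseline is to be captured as an adverse event and thus included in the summary of adverse events". This sentence has no worsening condition.

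**The concern.** The reason that 8.3.1.1 gives does not lead to its conclusion. If AE collection opens at the first dose, the natural reference is the last sample before that dose. The schedule provides one on Day 1, yet the protocol names the earlier sample.

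Sites therefore decide whether a result has worsened by looking back to Screening, while the SAP tabulates change and shift from Day 1. Anything that changes between the two samples happened without study drug, but under the site's rule it looks like a change since baseline.

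Frequency and severity of AEs and clinical laboratory tests are both listed under the primary safety objective. The study has a single arm, so no control group would show a similar background rate of such events. A pre-drug change that enters the AE table is simply read as an event on ANC-501.

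**Working it through.** The plan gives no figure to reproduce. The check sets the two rules against the laboratory schedule.

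**Step 1: which sample each rule uses.**
- Protocol 8.3.1.1: Screening, 1 to 30 days before Day 1.
- SAP 5.2 with the schedule: the Day 1 pre-dose sample, or Screening if Day 1 is missing. The SAP does not name Day 1; this follows from its definition and the visit schedule.

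**Step 2: where the rules part.** Take one analyte as Normal (N) or High (H) at Screening, Day 1 pre-dose and Day 8, which gives 2 × 2 × 2 = 8 patterns. The protocol column asks whether Day 8 is out of range and worse than Screening. The SAP column gives the shift from Day 1 to Day 8.

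| Screening | Day 1 pre-dose | Day 8 | Worse than protocol baseline? | SAP shift | Agree? |
|---|---|---|---|---|---|
| N | N | N | No | N to N | Yes |
| N | N | H | Yes | N to H | Yes |
| N | H | N | No | H to N | Yes |
| N | H | H | **Yes** | **H to H** | **No** |
| H | N | N | No | N to N | Yes |
| H | N | H | **No** | **N to H** | **No** |
| H | H | N | No | H to N | Yes |
| H | H | H | No | H to H | Yes |

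The rules differ in 2 of the 8 patterns. These are possible patterns, not probabilities. The pattern that carries the problem is N-H-H, where the whole change precedes the first dose.

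**Step 3: whether N-H-H becomes treatment-emergent.** Suppose the investigator judges the Day 8 value clinically significant. It then meets the 8.3.1.1 rule. SAP 9.2.1 counts AEs occurring after dosing, so the result depends on the recorded onset:
- Onset Day 8: after dosing, so treatment-emergent.
- Onset Day 1 with no time: SAP 5.1 imputes 23:59, after dosing, so treatment-emergent.
- Onset Day 1 with a time before dosing: not treatment-emergent unless it worsened.

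Two of the three ways of dating the event place a pre-drug change in the tables.

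**Step 4: whether a common baseline alone is enough.** The laboratory AE trigger is worded in three ways:
- Protocol 8.3.1.1: out of range, worse than baseline, and clinically significant.
- Protocol 8.4.1.1: out of range and clinically significant; worsening is included but not required.
- SAP 9.2.4: any clinically significant result after baseline.

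Under the second and third wordings, an N-H-H value on Day 8 still qualifies even when baseline is Day 1. The baseline and the trigger have to be settled together.

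**Step 5: size.** The documents give no rate for N-H-H or for a finding of clinical significance. One affected subject among 20 would be 1/20 = 5%.

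**The case against.** The strongest reply is that other sections already limit the problem.

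- **Recording window.** Protocol 8.4.3 opens AE recording at dosing on Day 1, so the Day 1 pre-dose result is not itself an AE. This stands for that sample. But 8.4.3 refers laboratory events back to 8.3.1.1, and the Day 8 result lies inside the window.
- **Pre-existing conditions.** Protocol 8.4.1.2 excludes expected fluctuation of conditions found at study start that do not get worse. An investigator could apply this to a stable N-H-H abnormality. It conflicts with 8.3.1.1, which says the same value has worsened, and nothing says which section governs.
- **Eligibility.** Inclusion criterion 3 requires that the subject "has no clinically significant findings, as determined by the Investigator, on physical examination, 12-lead electrocardiogram (ECG), vitals, or clinical laboratory tests", and criteria are reviewed again on Day 1. This helps only if Day 1 results are known before dosing, which the documents do not state. SAP section 4 changes the efficacy population because of two subjects discontinued after a failed Day 1 drug screen. Both efficacy definitions require a dose, so these subjects had apparently been dosed. That is an inference, and from a different test.
- **Precedence.** SAP section 11 lets the SAP prevail. This settles the analysis baseline but does not change what sites enter under the protocol.
- **Different measures.** Shift tables use reference ranges, while laboratory AEs need a judgement of clinical significance. The two would sometimes differ even under one baseline. This is right, so disagreement alone is not the complaint. The complaint is that a stated rule attributes a pre-drug change to the treatment period.

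Two stronger readings are tempting, and the documents do not support them. A reader might infer from H-N-H that real on-drug changes go unreported. Protocol 8.4.1.1 and SAP 9.2.4 do not require worsening, so a clinically significant Day 8 value is still reportable. A reader might also infer that screening results escape clinical review. The exemption sits in the AE-reporting section, which itself ends by requiring evaluation of every out-of-range value, and inclusion criterion 3 independently needs that review.

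**Conclusion.** The point holds in a limited form. The protocol and SAP use different laboratory baselines. As a result, a clinically significant abnormality that is new in the Day 1 pre-dose sample and persists to Day 8 can be reported as a treatment-emergent event on ANC-501, while the SAP shift table shows no change.

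This needs four things to coincide: the Day 1 sample is taken before dosing as scheduled; its result is unknown or not acted on at dosing; the investigator judges the later value clinically significant; and the site applies 8.3.1.1 rather than the exclusion in 8.4.1.2. With up to 20 subjects and descriptive safety summaries, the number affected is probably small.

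A reader might try to size it by multiplying analytes, subjects and an assumed rate of category change. The documents support no such rate, and the product would count changes of baseline category rather than AEs. The case for acting is that the rule is explicit, the study has no control arm, and the correction is cheap.

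**What to change.** 1. **Protocol 8.3.1.1.** Define the laboratory baseline for AE assessment as the most recent non-missing result before first dose: Day 1, or Screening if Day 1 is missing. This matches SAP 5.2. Naming Day 1 alone would lose the fallback.
2. **Pre-dose abnormalities.** State that laboratory abnormalities present before first dose are recorded as medical history and become AEs only if they worsen after dosing. SAP 9.2.5 already sends pre-dose physical examination findings to medical history.
3. **Trigger.** Reconcile protocol 8.3.1.1, protocol 8.4.1.1 and SAP 9.2.4 so that all three say the same about worsening. The timing phrase in 9.2.4 needs no change, because 5.2 already defines baseline.
4. **Subjects already dosed.** Before database lock, compare each reported laboratory AE with the Day 1 pre-dose value and query those already present then. Document the outcome in the clinical study report.

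No new samples are needed. A protocol amendment needs IRB approval under section 11.3 and will not alter AEs already entered. The SAP shows that dosing had begun, so step 4 is needed in any case, and it would be the main remedy if enrolment has finished.
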